2.2 Application

The topical product to be applied is then applied to the skin. Exactly 3g of product is used for this purpose.

SUPSI

The amount of product is evenly distributed in the application area with a glove until it can no longer be spread.

2.3 Follow-up measurement

After the application of the topical product, the first follow-up measurement is taken directly at time 0min, followed by further follow-up measurements every 10 minutes (time 10min post-application, 20min, 30min, 40min, 50min, 60min).

2.4 Conclusion and compensation

After the last follow-up measurement at 60 minutes, the experiment is over for the test subject. He/she will receive the amount due to him/her according to the advertisement.

The lump sum is 50.-CHF.

SUPSI

10 SAFETY

Clinical trial with a medical device in the risk category Cat. **A** KlinV (Art. 20)

The subjects are given topical products available over the counter with a warming effect or cooling effect locally. No other medication is dispensed. Nor are tissue samples taken or invasive (measurement) methods used.

No further security aspects are expected.

10.1 Drug study

The products used are available without a prescription, the warming substances are based on wintergreen oil, the cooling ones on menthol and/or alcohol.

10.1.1 Definition and assessment of (serious) adverse events and other safety related events

-

10.1.2 Reporting of serious adverse events (SAE) and other safety related events

-

10.1.3 Follow up of (Serious) Adverse Events

-

10.2 Medical Device Category C studies

-

10.2.1 Definition and Assessment of (Serious) Adverse Events and other safety related events

-

10.2.2 Reporting of (Serious) Adverse Events and other safety related events

-

10.2.3 Follow up of (Serious) Adverse Events

-

10.3 Medical Device Category A studies

This study is a category A clinical observational study in accordance with the Swiss Ordinance on Clinical Trials in Human Research (ClinO, Art. 20).

It is a study with 40 subjects. The study focuses on basic findings. The monitoring for quality assurance is carried out by [name]. [name].

10.3.1 Definition and recording of safety-relevant events

An adverse event (ADVERSE EVENT) AE) is any unfortunate medical occurrence in a study subject who is exposed to a single application of a topical product (as listed in Chapter 8.1.1) that is not necessarily causally related to the study process. An AE can therefore be any adverse and unintended sign, symptom, or temporal illness with the use of an intervention product (according to Chapter 8.1.1), either or in relation to the medical intervention product (according to Chapter 8.1.1). The package leaflets

SUPSI

of the products used here describe possible side effects. These include skin itching, redness, burning as occasional side effects, eczematous skin lesions as rare and pronounced hypersensitivity reactions as very rare side effects.

According to swissethics.ch, a serious adverse event (SAE) is classified as any unfortunate medical occurrence that results in death, is life-threatening, requires or prolongs hospitalization of the subject, results in a persistent or significant disability/inability, or is a congenital anomaly/birth defect. In our study, SAE is not expected due to the possible side effects described in the product package inserts and/or product patient information.

The topical products used in this study are applied according to their package leaflet (not on mucous membranes, open, bleeding wounds / not near the eyes / not in case of hypersensitivity to one ingredient / not in subjects with bronchial asthma / not in subjects with renal insufficiency / not in children, pregnant women, during breastfeeding / do not cover with bandage or compress / do not cover several preparations at the same time on the same skin area). The contraindications and precautions described in the respective package leaflets are taken into account in the health questionnaire and the screening test. Thus, possible vulnerable subjects are recorded before the actual product application and excluded from the study. In addition, the one-time product application is below the recommended dosage according to the package inserts (massage briefly several times a day (max. five times) in a thin layer without pressure / rub in a sufficient amount on desired parts of the body).

If the application of the topical product leads to a side effect described above, this is classified as a safety-relevant event by the study leader. For the affected study participant, the study is completed at this time, and the data already collected will be processed as described in chapters 7.4 and 9.1.6.

The subject-specific demographic data collection sheet (page 4) records:

- Date and time of the incident
- Course of the incident
- Persons involved & witnesses
- Study ID (specified by the CEC)
- Personal data of the person concerned (if not previously recorded)

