2.9 Early termination of the study

The sponsor or principal investigator may discontinue the study early if/

- ethical concerns
- insufficient number of subjects
- the safety of the participants cannot be guaranteed
- Findings from clinical practice make it pointless to continue the study
- early evidence or harm of the experimental intervention has been proven

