9.1.6 Collection of data in case of early termination of studies

For the participants, there is no disadvantage in the event of an (arbitrary) discontinuation of study participation and no further interventions are necessary for follow-up treatment. The data collected to date will be evaluated as far as possible and included in the data analysis (in accordance with Art. 9 ClinO).

SUPSI

However, if study participation was discontinued due to an excessive skin reaction occurring during study participation, this will be recorded and reported to the sponsor investigator (head of the research laboratory), study management and supervisor of the study. In the event of necessary medical treatment, the report is sent to the business liability insurance of Thim van der Laan AG (Basler Versicherung).

The following are recorded:

- Date and time of the incident
- Course of the incident
- Persons involved & witnesses
- Study ID (specified by the CEC)
- Personal data of the person concerned (if not previously recorded)

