11.4.5 Security analyses

No security analyses are provided.

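### The recording trigger in 10.3.1 is narrower than its own adverse-event definition, and no safety table or cumulative count is planned to support the harm reason in 2.9

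*Combined protocol and SAP*

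**What the plan says.** Section 10.3.1 starts broadly. An adverse event is "any unfortunate medical occurrence in a study subject" exposed to a study product, with no causal link required, and the section adds: "An AE can therefore be any adverse and unintended sign, symptom, or temporal illness with the use of an intervention product". It then summarises the package leaflets: "These include skin itching, redness, burning as occasional side effects, eczematous skin lesions as rare and pronounced hypersensitivity reactions as very rare side effects".

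The rule that leads to a record comes next: "If the application of the topical product leads to a side effect described above, this is classified as a safety-relevant event by the study leader". The study ends at that point for that participant. The incident goes on page 4 of the demographic data sheet: date and time, course, people involved and witnesses, study ID and personal data. The data already collected are to be handled under 7.4 and 9.1.6. Section 10.3.3 sends each such event at once to the sponsor-investigator, study management and supervisor, then to the ethics committee and the liability insurer.

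A second route stands in 9.1.6, with a parallel in 8.5: "if study participation was discontinued due to an excessive skin reaction occurring during study participation, this will be recorded and reported".

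Sections 5.3 and 9.1.5 say that, apart from screening items, nothing further is collected for safety. Section 11.4.5 reads: "No security analyses are provided". Section 11.4.4 plans no interim analysis. Section 2.9 nevertheless lets the sponsor or principal investigator stop the study when "early evidence or harm of the experimental intervention has been proven".

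**The concern.** The definition and the trigger do not match. The trigger asks for a side effect already described and for the application to have led to it. An event that is unlisted, or not judged causal, meets the definition but no sentence says that it is written down. The familiar reactions are then recorded and an unfamiliar one may not be, although an unfamiliar one would tell the sponsor more.

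The analysis plan adds nothing downstream. Eight products are tested (8.1.1), yet no table of events by product is planned, and the listed incident fields do not name the product. The final report would have no planned statement on tolerability, and a decision about harm under 2.9 would have single reports to go on but no running count.

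**Working it through.** The plan states no safety rate, threshold or precision, so there is no figure to reproduce. The check is a reading of the passages, followed by a calculation for scale.

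**1. Trace one event.** Take dizziness on rising after the prone session, in a participant who has finished the measurements.
- 10.3.1, definition: met.
- 10.3.1, trigger: not met on the natural reading, since dizziness is not among the leaflet effects described.
- 8.5 and 9.1.6: not met. It is not a skin reaction and did not end participation.
- 6.3: mentions adverse events before and after 24 hours, but decides when blinding may be lifted. It gives no recording step.
- 10.3.2: cites three articles without saying what is recorded.
- 5.3 and 9.1.5: no other safety data are collected.

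No recording step remains. The same holds for a forearm-test reaction: the Synopsis (Preparation) and 3.7 exclude the person but do not say that the reaction is recorded.

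**2. Can recorded events be counted by product?** Product and side are noted on the drawn lot (7.3). If a participant withdraws, 7.4 returns that lot to the pot in a new envelope. The page 4 fields listed in 10.3.1 do not carry the product. For participants who stop, the protocol names no place where event and product stand together.

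**3. What happens to the data of affected participants?** 10.3.1 refers to 7.4 and 9.1.6, which evaluate and include data collected so far. Sections 8.5 and 11.5 destroy the data of those who do not complete, and 11.3 and 11.4.1 admit completers only. These rules cannot all be followed.

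**4. Redness.** Redness is a listed effect, so under 10.3.1 it ends participation. Erythema is also a primary outcome (Synopsis; 5.1). Read literally, a participant who shows the response under study is stopped, and 11.3 then removes that participant from the analysis.

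**5. Scale.** Inputs: 2 × 45 + 15 = 105 participants (Synopsis; 6); three warming products, one of them also used for the 15 sub-analysis participants (8.1.1). Assumption: the 45 warming participants are split equally, 45 / 3 = 15 per product. The sub-analysis product then has 15 + 15 = 30.

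The exact one-sided 95% upper bound for zero events in n is 1 − 0.05^(1/n):
- n = 15: 1 − 0.05^(1/15) = 18.1%
- n = 30: 1 − 0.05^(1/30) = 9.5%
- n = 105: 1 − 0.05^(1/105) = 2.8%

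The chance of at least one case is 1 − (1 − p)^n. For assumed true rates of 0.1%, 1% and 5% it is 10%, 65% and 99.5% in 105 participants. At 1% it is only 14% in 15. A rare reaction would show up once or not at all.

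Separating products is another matter. With 15 per product, Fisher's exact two-sided p for 0 against 4 events is 2 × C(15,4)/C(30,4) = 2 × 1365/27405 = 0.0996. For 0 against 5 it is 2 × 3003/142506 = 0.042. A difference of zero against one third would be needed.

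Section 10.3 speaks of 40 participants, which does not agree with 105 and should be corrected with the rest of the section.

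**The case against.** A reader might infer that only leaflet effects can ever be recorded. The documents do not support that. Sections 8.5 and 9.1.6 are an additional route and record an excessive skin reaction whether or not a leaflet lists it. The leaflet list is open-ended and names hypersensitivity reactions in general, so an allergic respiratory reaction could fall within it. The words of the trigger could even be stretched to the whole definition. What stands is that non-skin events, and events not judged causal, are covered on no clear reading.

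A reader might also infer that harm under 2.9 can never be assessed. That is too strong. Section 10.3.3 passes each classified event on at once, 12.4 provides a monthly oral report that includes results, and 2.9 also allows stopping when participants' safety cannot be guaranteed. Case-by-case judgement is possible. What is missing is a cumulative summary.

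The lot does record the product, so events in completers could be tabulated later. That is fair, but it does not cover participants whose lot goes back to the pot and whose data 11.5 destroys. The page 4 sheet, the other data forms and the text of the cited articles were not available, and they may hold more than the protocol states.

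Finally, tolerability is not an objective, and the intervention is one application of an over-the-counter product in screened healthy adults. That lowers the weight of the point. It does not explain a trigger narrower than the definition in the same section.

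**Conclusion.** The point holds in limited form. Followed as written, 10.3.1 gives an incomplete safety record: an unlisted, non-skin event has no recording step, the product is absent from the listed incident fields, and no table or cumulative count is planned. This should be changed, but it does not threaten the trial's main comparisons.

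Its size cannot be given as a rate, because the plan contains none. The upper bounds of 18.1%, 9.5% and 2.8% show only how little a count of zero would exclude. They follow from the sample sizes, not from the recording rule, and rest on an equal split that the protocol does not state. No figure is given for the other five products, because the split among them, including the three that cool and then warm, is not described. The actual number exposed may also differ from 105. A table by product would describe tolerability and would rarely separate one product from another.

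**What to change.** 1. **10.3.1:** record on page 4 every event that meets the section's own definition, listed in a leaflet or not, with product, body site, onset time and whether participation ended.
2. **11.4.5:** replace the present sentence by a descriptive table of the number of participants with each event, by product, over all exposed participants including those who stop, with exact confidence intervals. Show forearm-test reactions separately with their own denominator, since people excluded at screening belong in it.
3. **2.9:** state that the cumulative counts go to the role that decides on early termination.
4. **10.3.3:** leave the notification chain as it is for safety-relevant events. Sending every minor, unrelated event to all recipients, including the insurer, would go beyond the defect.
5. **Reconcile:** 7.4, 9.1.6 and the reference to them in 10.3.1 with 8.5, 11.3, 11.4.1 and 11.5 on the data of affected participants; and the ending of participation for listed redness in 10.3.1 with erythema as a primary outcome. The table in item 2 works only if event records of participants who stop are retained.

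The cost is wording in a few sections, a few fields on an existing form and one table. No visits or measurements are added.

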10.3.2 Reporting of Safety related events

In accordance with Art. 37, Art. 42, Art. 43

10.3.3 Notification of a security-relevant event

A safety-related event is logged and immediately reported to the sponsor investigator (head of the research laboratory), study management and supervisor of the study.

The CEC will be informed as soon as possible and appropriate changes will be made to the protocol of the study. Further explanations can be found in chapter 2.10. Safety and protective measures must be reported to the responsible CEC within two days.

The report continues to the business liability insurance (Basler Versicherung) of Thim van der Laan AG in Landquart.

SUPSI

11 STATISTICAL METHODS

11.1 Hypotheses & Factors

*Local change in skin characteristics during and after a topical application of a **warming** product*

Perfusion of skin microcirculation

- H0 The perfusion of the skin microcirculation does not change significantly during and after the topical application of a warming product to the collateral side.
- H1 The perfusion of the skin microcirculation changes significantly during and after the topical application of a warming product to the collateral side.

Erythema formation

- H0 Erythema formation does not change significantly during and after topical application of a warming product to the collateral side.
- H1 Erythema formation changes significantly during and after topical application of a warming product to the collateral side.

Skin surface temperature

- H0The skin surface temperature does not change significantly during and after the topical application of a warming product to the collateral side.
- H1The skin surface temperature changes significantly during and after the topical application of a warming product compared to the collateral side.

Oxygen saturation of the superficial muscles

- H0The oxygen saturation of the superficial muscles does not change significantly during and after the topical application of a warming product to the collateral side.
- H1The oxygen saturation of the superficial muscles changes significantly during and after the topical application of a warming product to the collateral side.

Subjective temperature perceptions

- H0The subjective temperature perception does not change significantly during and after the topical application of a warming product to the collateral side.
- H1The subjective temperature perception changes significantly during and after the topical application of a warming product compared to the collateral side.

*Local change in skin characteristics during and after a topical application of a **cooling** product*

Perfusion of skin microcirculation

- H0 The perfusion of the skin microcirculation does not change significantly during and after the topical application of a cooling product to the collateral side.

SUPSI

- H1 The perfusion of the skin microcirculation changes significantly during and after the topical application of a cooling product to the collateral side.

Erythema formation

- H0 Erythema formation does not change significantly during and after topical application of a cooling product to the collateral side.
- H1 Erythema formation changes significantly during and after topical application of a cooling product to the collateral side.

Skin surface temperature

- H0 Skin surface temperature does not change significantly during and after topical application of a cooling product to the collateral side.
- H1 The skin surface temperature changes significantly during and after the topical application of a cooling product with respect to the collateral side.

Oxygen saturation of the superficial muscles

- H0The oxygen saturation of the superficial muscles does not change significantly during and after the topical application of a cooling product to the collateral side.
- H1The oxygen saturation of the superficial muscles changes significantly during and after the topical application of a cooling product to the collateral side.

Subjective temperature perceptions

- H0The subjective temperature perception does not change significantly during and after the topical application of a cooling product to the collateral side.
- H1The subjective temperature perception changes significantly during and after the topical application of a cooling product compared to the collateral side.

A 2-factor analysis is carried out.

Factor 1: Intervention (warming product versus control / cooling product versus control)

Factor 2: Time (baseline, 0min, 10min, 20min, 30min, 40min, 50min, 60min postal application)

11.2 Sample size

The sample size in the literature varies greatly. The planned number of 105 subjects is within the wide range and is expedient, time-wise and financially feasible for the study.

11.3 Criteria for the statistical use of data in the case of incomplete data sets

Only data from subjects who have completed the entire protocol will be included in the study. This ensures that all data has been collected under the same conditions and thus remains homogeneous and comparable.

SUPSI

11.4 Scheduled analyses

11.4.1 Datasets and Data Population

Only complete data sets will be included in the study. Data that contains only part of the protocol is not included in the analysis. No new test subject is being sought to replace the missing data.

11.4.2 Primary Analysis

The statistical data analysis will be carried out by [name] after completion of the data collection of the entire project.

Repeated measures analysis of variance (MANOVA)

2 factors:

Factor 1: Intervention (warming product versus control / cooling product versus control)

Factor 2: Time (baseline, 0min, 10min, 20min, 30min, 40min, 50min, 60min postal application)

The significance level is set at $P < 0.05$, and the statistical data analysis is carried out with SPSS V. 23.

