
Measurements and procedures:
	
After the 20-minute acclimatization phase, the application area is drawn (skin-friendly pen), the template (recess 10cm x 10cm) is applied and the baseline measurements (a-e) are performed. After the baseline measurement, the product is applied (3g)⁸. The product is applied until it can no longer be distributed. The research employee wears a glove. This is followed by the measurements (a-d) at 0min, 10min, 20min, 30min, 40min, 50min, 60min post-application.
 
a) Perfusion of skin microcirculation
 
The perfusion of the skin microcirculation is performed using the Laser Speckle Contrast Imager (moorFLPI 2, moor instruments, www.moor.co.uk), the High Power Laser Doppler (moorVMS-LDF1-HP, moor instruments, www.moor.co.uk) and the ultrasound X-Flow (esaote MyLabClassicC, Maastricht, Netherlands, www.esaote.com). Since the contact gel, which is required for the ultrasound X-Flow measurement, could interfere with the product application, or could interfere with the subjective temperature perception of the subject, the ultrasound measurement is only measured at the time of baseline and 60min post-application. This was after questioning the subjective parameters.
 
b) Erythema formation
 
Erythema formation is visualized using the chromameter (www.konicaminolta.eu). The chromameter measures the light reflection and absorption of the skin.
 
c) Skin surface temperature
 
The surface temperature of the skin is measured using an infrared thermometer (Votcraft InfraRed Thermometer, IR 800-20D) and the i-buttons. The iButton system consists of self-adhesive sensors that wirelessly transmit skin temperature information to a computer (www.ibuttonlink.com). In addition, a thermal imaging camera (www.csem.ch) records the skin surface temperature.
 
d) Oxygen saturation of the superficial muscles
 
The oxygen saturation of the superficial muscles is determined using the near-infrared measurement method (moorVMS-NIRS, moor instruments, www.moor.co.uk) The measurement is non-invasive and painless. The sensors are placed on the corresponding muscles.
 
e) Subjective Perception Parameters
 
The test subjects indicate their subjective temperature perception on a scale of 9 points from -4 (very cold) to +4 (very hot). They then rate the thermal comfort on a 5-point scale between 0 (pleasant) and 4 (extremely unpleasant)¹¹.
 
Further processing of the data
 
Windows uses Excel for data pooling and the graphical representation of the end data®.

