6.1 Method for minimizing influencing factors

6.1.1 Randomization

The area of application is randomized, right-sided or left-sided paravertebral lumbar. In addition, the assignment to the group "warming ointment" or group "cooling ointment" is hidden and randomized. The randomization procedure is carried out by lottery.

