8.2.2 Control intervention

The control intervention does not consist of any application, the selected skin area remains blanco. The lumbar paravertebral opposite side of the intervention site is taken as a control skin area.

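### The primary model enters baseline as one of eight outcome times and names no primary contrast; this can cost power for sustained effects, and the model as written cannot be fitted to X-Flow

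*Combined protocol and SAP*

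**What the plan says.** Section 11.4.2 names the method as "Repeated measures analysis of variance (MANOVA" and gives two factors: "Factor 1: Intervention (warming product versus control / cooling product versus control" and "Factor 2: Time (baseline, 0min, 10min, 20min, 30min, 40min, 50min, 60min postal application". The synopsis (Statistical Considerations) and section 11.1 list the same eight time levels. None of the three places names a baseline covariate, a change score or a primary contrast, and section 11.4.3 plans no secondary analysis.

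The comparison is within subject. Section 8.2.2: "The lumbar paravertebral opposite side of the intervention site is taken as a control skin area". Section 6.1.1: "The area of application is randomized, right-sided or left-sided paravertebral lumbar". A typical alternative hypothesis in section 11.1 reads: "The perfusion of the skin microcirculation changes significantly during and after the topical application of a warming product to the collateral side".

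X-Flow ultrasound is a primary perfusion measure (section 5.1). According to the synopsis (Measurements and procedures), however, "the ultrasound measurement is only measured at the time of baseline and 60min post-application". No separate model is given for it.

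**The concern.** The hypotheses ask whether the treated side changes relative to the untreated side of the same person. Two tests from the planned model could answer this, and they behave very differently.

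- **Side main effect.** It averages in a reading that the product cannot have affected, and a person's natural left-right difference stays in the error.
- **Side-by-time interaction.** It removes a stable left-right difference, because every contrast is a change from baseline. But it spreads the test over 7 degrees of freedom, and it subtracts baseline in full where a regression on baseline would subtract only the useful part.

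At stake are power in groups of 45 and 15, and the freedom to choose between the two tests after seeing the data. For X-Flow the planned model cannot be run as written.

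**Working it through.** **Inputs from the documents.** There are 45 subjects per warming or cooling class and 15 in the sub-analysis (45 + 45 + 15 = 105, the stated total). There are eight times, one of them before application. The side is randomised, so the expected baseline side difference is zero. The significance level is 0.05. Section 11.2 gives no power, effect size, SD or correlation, so there is no planned power to reproduce.

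**Assumptions.** Let D_t be treated minus control at time t, with SD 1 at every time. The correlation between times s and t is c + (1 − c) × 0.5^|s−t|, where c is the stable share, varied from 0.2 to 0.8. The main case is a constant effect of 0.35 SD at all seven post-application times.

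**Formulas, with n = 45 and c = 0.4.** Each noncentrality λ is n times the squared effect over its variance, or the matrix equivalent. Here n × 0.35² = 5.5125.

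1. Side main effect: the effect is 0.35 × 7/8 = 0.306 and the variance of the eight-time mean is 0.588. λ = 45 × 0.0938 / 0.588 = 7.2 on 1 and 44 df; power 0.75.
2. Planned interaction (Hotelling T² on the seven changes from baseline): λ = 11.0 on 7 and 38 df; power 0.57.
3. One-df mean change from baseline: variance 0.638, λ = 5.5125 / 0.638 = 8.6; power 0.82.
4. Seven-df test of the post-application differences with baseline as covariate: λ = 17.1 on 7 and 37 df; power 0.79 after allowing for chance imbalance in the observed baseline difference.
5. Mean of the seven post-application differences with baseline as covariate: residual variance 0.373, λ = 5.5125 / 0.373 = 14.8; power 0.96 after the same allowance.

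**Range over the unknown correlation** (n = 45, constant 0.35 SD):

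| Stable share | 0.2 | 0.4 | 0.6 | 0.8 |
|---|---|---|---|---|
| Planned interaction | 0.44 | 0.57 | 0.78 | 0.99 |
| Side main effect | 0.85 | 0.75 | 0.66 | 0.58 |
| Baseline-adjusted 7-df test | 0.76 | 0.79 | 0.88 | 0.99 |
| Baseline-adjusted post mean | 0.96 | 0.96 | 0.98 | 1.00 |

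The two planned readings move in opposite directions. Under equal correlation r between all times this has a closed form for a constant effect. The interaction keeps (1 + 7r)/8 of the information in the adjusted 7-df test: 0.30, 0.56, 0.74 and 0.91 at r = 0.2, 0.5, 0.7 and 0.9. The main effect keeps 7(1 − r)/8 of the information in the adjusted mean: 0.70, 0.44, 0.26 and 0.09.

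**Other effect shapes** (n = 45). For an effect fading from 0.35 to 30% of that, with c = 0.4, power is 0.52 for the interaction, 0.40 for the main effect and 0.68 for the adjusted mean. With c = 0.8 the interaction has 0.97 and the adjusted mean 0.93. For an effect running linearly from −0.35 to +0.35 SD, with c = 0.4, the interaction has 0.91 and the adjusted mean 0.05.

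**Sub-analysis** (n = 15, constant 0.65 SD, c = 0.4): interaction 0.38, main effect 0.76, adjusted mean 0.95.

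**X-Flow.** Six of eight time cells are empty on each side for every subject. A two-level version (baseline, 60 min) can be fitted. Its side-by-time test has efficiency (1 + r)/2 relative to adjusting for baseline: 0.60, 0.75, 0.85 and 0.95 at the same four values of r.

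**The case against.** The strongest defence is that the hypotheses speak of change relative to the other side, which is most naturally the interaction. That test is valid and already cancels a stable left-right difference. This stands. A reader might infer that the plan ignores its baseline or gives a biased answer; the documents support neither. What they leave out is a statement that the interaction is the primary test.

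Second, setting 0.57 against 0.96 compares a 7-df test with a 1-df test. This also stands. Of the 0.39 gap, adjustment for baseline accounts for 0.14 (0.96 − 0.82, both on 1 df) or 0.22 (0.79 − 0.57, both on 7 df), depending on the order. The rest comes from concentrating the test on one contrast.

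Third, readings from one session on a fixed site may be highly correlated, and then the interaction loses little; for a fading effect it can even beat the adjusted mean. The documents cannot settle the correlation.

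Fourth, section 8.1.1 includes three products (of eight) said to cool and then warm. A one-hour mean could miss their effect entirely, so it cannot be the primary contrast for every product.

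A reader might also take the word MANOVA to mean one joint model over all outcomes, with more contrasts than the sample supports. The documents do not support that: section 11.1 states a separate pair of hypotheses for each outcome, and no joint model is described. The multivariate approach to repeated measures, outcome by outcome, is the natural reading, and it can be fitted for outcomes measured at all eight times.

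**Conclusion.** The point holds as one of efficiency and clarity; it should be changed. Three parts need no assumption: baseline is an outcome level with no adjustment, no primary contrast is named, and the eight-level model cannot be fitted to X-Flow.

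The power loss depends on assumptions that the documents do not supply. For a constant 0.35 SD effect with 45 subjects, the like-for-like gain from adjusting the 7-df test runs from 0.32 (0.76 against 0.44) at a stable share of 0.2 to practically nothing at 0.8. If the main effect were used, its shortfall against the adjusted mean would run from 0.11 (0.96 − 0.85) to 0.42 (1.00 − 0.58). For effects that average zero over the hour, adjustment gains nothing.

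**What to change.** For each outcome, analyse treated minus control at the seven post-application times, with the subject's baseline side difference as covariate, evaluated at zero baseline difference (the expected value, because the side is randomised). Name the primary contrast in advance:

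- for products expected to act in one direction, including the hot gel of the sub-analysis: the mean post-application side difference;
- for the cool-then-warm products, and for any analysis that pools them with others: the baseline-adjusted joint test of the seven times.

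Analyse X-Flow as the 60-minute side difference adjusted for its baseline difference. State that the analysis is done outcome by outcome.

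The cost is analysis wording; no new data are needed, and the planned software can fit these models. There are two downsides. The mean misses effects that reverse sign, so the time-specific differences should still be reported. The adjusted 7-df test gives up one error df (7 instead of 8 at n = 15) and can then be somewhat weaker than the planned interaction. The overview already reports preliminary warming results, so for those data the change should be recorded, under section 11.4.6, as made after they were seen.
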